1 GLOSSARY OF TERMS

Table 1-1 List of Terms

Term	Definition
Adverse Drug Reaction (ADR)	All noxious and unintended responses to an investigational product related to any dose should be considered adverse drug reactions. Responses to a medicinal product means that a causal relationship between a medicinal product and an adverse event is at least a reasonable possibility, i.e., the relationship cannot be ruled out.
Adverse Event (AE)	Any untoward medical occurrence in a subject or clinical investigation subject administered a pharmaceutical product and which does not necessarily have a causal relationship with this treatment. An AE can therefore be any unfavorable and unintended sign (including an abnormal laboratory finding), symptom, or disease temporally associated with the use of an investigational product, whether or not related to the investigational product.
Device Deficiency	Inadequacy of a medical device with respect to its identity, quality, durability, reliability, usability, safety, or performance. Note: This definition includes malfunctions, use errors, and inadequacy in the information supplied by the manufacturer including labelling related to the investigational medical device.
Enrollment	A human subject's, or their legally authorized representative's, agreement to participate in a clinical trial following completion of the informed consent process, as required in 21 CFR part 50 and/or 45 CFR part 46, as applicable. For the purposes of this part, potential subjects who are screened for the purpose of determining eligibility for a trial, but do not participate in the trial, are not considered enrolled, unless otherwise specified by the protocol. A subject is enrolled at the time point they begin receiving the study investigational product.
Interventional Clinical Trial	Clinical trial in which subjects are assigned to groups that receive one or more intervention/treatment (or no intervention) so that researchers can evaluate the effects of the interventions on biomedical or health-related outcomes. The assignments are determined by the study's protocol. Subjects may receive diagnostic, therapeutic, or other types of interventions.
Investigational Product	A preventative (vaccine), a therapeutic (drug or biologic), device, diagnostic, or palliative used as a test or comparator product in a clinical study, including a product with a marketing authorization when used or assembled (formulated or packaged) in a way different from the authorized form, or when used for an

Term	Definition
	unauthorized indication, or when used to gain further information about the authorized form.
Nonserious Adverse Event	Adverse event that does not meet the criteria for a serious adverse event.
Point of Enrollment	The time at which, following recruitment and before any clinical investigation-related procedures are undertaken, a subject signs and dates the informed consent form.
Screen Failure	A subject who did not meet one or more criteria that were required for participation in the study.
Screening	A process of active evaluation of potential subjects for enrollment in a study. After a patient is recruited, screening occurs during the enrollment period, after informed consent has been obtained, to see if they meet the inclusion and exclusion criteria. If they meet the criteria, the subject is eligible to enroll in the study.
Serious Adverse Event (SAE)	
Any untoward medical occurrence that at any dose:
 
 results in death, is life-threatening, 
Note: Life-threatening means that the individual was at immediate risk of death from the event as it occurred, i.e., it does not include an event which hypothetically might have caused death had it occurred in a more severe form.
 
 requires inpatient hospitalization or prolongation of existing hospitalization, 
Note: Planned hospitalization for a preexisting condition, without serious deterioration in health, is not considered a serious adverse event.
 
 results in persistent or significant disability/incapacity, is a congenital anomaly/birth defect, or is a medically important event or reaction. 
Note: Medical and scientific judgment should be exercised in deciding whether other situations should be considered as serious such as important medical events that may not be immediately life-threatening or result in death or hospitalization but may jeopardize the patient or may require intervention to prevent one of the other outcomes listed in the definition above. These should also be considered serious.

Term	Definition
	Examples of such events are intensive treatment in an emergency room or at home for allergic bronchospasm; blood dyscrasias or convulsions that do not result in hospitalization; or development of drug dependency or drug abuse.
Serious Adverse Reaction (SAR)	Adverse drug reaction that has resulted in any of the consequences characteristic of a serious adverse event.
Study Completion	The completion of the study is considered to coincide with the study-level last subject last visit or the decision to terminate the study, whichever is later.
Study Start	The start of the study is considered to coincide with the enrollment of the first patient.
Subject	A study participant
Suspected Unexpected Serious Adverse Reaction (SUSAR)	Adverse drug reaction that is both unexpected and meets the definition of a serious adverse event.
Unexpected Adverse Drug Reaction (Unexpected ADR)	An adverse reaction, the nature or severity of which is not consistent with the applicable product information (e.g., investigator's brochure for an unapproved investigational product or Company Core Data Sheet and/or package insert/summary of product characteristics for an approved product).

Table 1-2 List of Acronyms and Abbreviations

Abbreviation	Definition
ADDE	Aqueous deficient dry eye
ADR	Adverse drug reaction
AE	Adverse event
AR	Adverse reaction
BCVA	Best corrected visual acuity
°C	Degrees Celsius
CI	Confidence intervals
CL	Confidence limits
CONSORT	Consolidated standards of reporting trials
CRF	Case Report Form
CRO	Contract Research Organization
DED	Dry eye disease

Abbreviation	Definition
DEP	Data evaluability plan
DES	Dry eye symptom
█	█
EC	Ethics Committee
eCRF	Electronic case report form
ePRO	Electronic patient reported outcomes
EDC	Electronic data capture
EDE	Evaporative dry eye
EN	European Standard
EU	European Union
ETDRS	Early Treatment Diabetic Retinopathy Study
FID	Formulation identification
GCP	Good Clinical Practice
Hr	Hour(s)
ICE	Intercurrent event
ICF	Informed consent form
IB	Investigator's brochure
ICH	International Conference on Harmonisation of Technical Requirements for Pharmaceuticals for Human Use
IDEEL-SB	Impact of Dry Eye on Everyday Life- Symptom Bother
IEC	Independent Ethics Committee
IFU	Instructions for use
IP	Investigational product
IRB	Institutional Review Board
LogMAR	Log of the minimum angle of resolution
MDE	Mixed dry eye
mL	milliliter
█	█
MOP	Manual of procedures
N/A	Not applicable
█	█
OD	Right eye
OS	Left eye
OTC	Over the counter

Abbreviation	Definition
PP	Per Protocol
SAE	Serious adverse events
SAR	Serious adverse reaction
SD	Standard deviation
SLE	Slit lamp examination
SOC	Standard of care
SUSAR	Suspected unexpected serious adverse reaction
████	████████████████
US	United States

2 PROTOCOL SUMMARY

2.1 Protocol Synopsis

Compound Number(s):	FID123300
Study Phase:	Phase 3
Brief Summary of Protocol:	A 30-day prospective, single-arm, multicenter, open label study to demonstrate efficacy and safety of a novel lubricant eye drop in adult patients with mild to moderate dry eye disease (DED).

2.1.1 Primary and Safety Objectives and Endpoints

Table 2-1 lists the objectives and endpoints. For more information, see Section 4.

Table 2-1 Primary and Safety Objectives and Endpoints

Primary Objective	Primary Endpoint
To demonstrate efficacy of a novel lubricant eye drop	Change from baseline in Impact of Dry Eye on Everyday Life - Symptom Bother (IDEEL-SB) questionnaire score at Day 30
Safety Objective	
 • Adverse events • BCVA • Biomicroscopy findings • Device deficiencies
To evaluate safety of a novel lubricant eye drop	

2.1.2 Overall Design

Several key aspects of the study design are summarized below.

Intervention Model:	Single group
Control:	None/uncontrolled
Active Comparator:	N/A
Interventional Product Assignment Method:	All subjects will receive the same investigational product (IP)
Population Type:	Adult subjects

Population Age:	Minimum: 18 – Maximum: N/A
Number of Subjects:	~185 enrolled
Number of Arms:	1
Site Distribution:	Planned number of clinical sites: ~ 20 Planned locations: United States

2.1.3 Arms and Duration

Total duration of study participation for each subject: approximately 37 days.

2.1.4 Masking

The following roles indicated below will not be made aware of the intervention assignment during the study:

- N/A (no masking)

For more information on masking, see Section 7.6.

[figure not shown]
2.1.5 Committees

N/A

2.2 Study Schema

Figure 2-1 illustrates the study design.

Figure 2-1 Study Design

2.3 Schedule of Study Procedures and Assessments

Table 2-2 provides a summary of the schedule of study procedures and assessments.

Table 2-2 Schedule of Study Procedures and Assessments

Visit	Visit 1 Screening	Visit 2 Baseline	Visit 3 Remote Compliance Check	Visit 4 Exit	Unscheduled Visit	Early Exit
Study Day and Visit Window	2 to 7 days prior to Visit 2	Day 1	Day 14 ± 3 days	Day 30 ± 5 days		
Informed consent	X					
Connect to electronic patient reported outcomes	X ⁹	X		X	(X)	X
Demographics	X					
Medical history	X					
Concomitant medications	X					
Changes to concomitant medications or medical history		X	X	X	X	X
Urine pregnancy test ¹	X			X	(X)	X
Inclusion/exclusion	X					
Meibomian gland functionality test ¹	X					
BCVA (OD, OS; logMAR; distance)	X	X		X	(X)	X
IDEEL-SB Questionnaire ⁸	X			X		X

Visit	Visit 1 Screening	Visit 2 Baseline	Visit 3 Remote Compliance Check	Visit 4 Exit	Unscheduled Visit	Early Exit
Study Day and Visit Window	2 to 7 days prior to Visit 2	Day 1	Day 14 ± 3 days	Day 30 ± 5 days		
Slit lamp biomicroscopy examination (with corneal staining)	X	X		X	X ⁷	X
Administer IP (IP instillation on site)		X				
Adverse events	X	X	X	X	X	X
Device deficiencies	X	X	X	X	X	X
Distribute subject instructions		X			(X)	
Dispense IP		X			(X)	
Collect used and unused IP				X	(X)	X
Remote compliance check			X			

(X) Assessments performed as necessary

¹ Source Only

⁷ Assessment performed as necessary for unplanned dispense visit

⁸ Electronic patient reported outcomes unless otherwise specified by sponsor

⁹ Screening may be rescheduled within 7 days/1 week if connection cannot be established. All remaining criteria will be verified after completing connection.

3 INTRODUCTION

3.1 Purpose of Study

The novel formulation (FID123300) is aimed at providing long-lasting comfort to patients with dry eyes. The study is designed to evaluate and demonstrate the efficacy and safety of this investigational ocular lubricant formulation in patients with mild to moderate DED.

Endpoints include safety assessments (AEs, BCVA, slit lamp biomicroscopy, and device deficiencies), subjective assessment of symptoms of dry eye (IDEEL-SB [REDACTED])

[REDACTED]
[REDACTED]
[REDACTED].

Refer to Sections 2.2 and 2.3 for more information.

3.2 Summary of Benefits and Risks

3.2.1 Benefit Summary

The key benefit expected from the novel ophthalmic lubricant is the temporary relief of dry eye symptoms in patients with dry eye similar to other currently marketed dry eye drops such as SYSTANE COMPLETE Lubricant Eye Drops [REDACTED] and SYSTANE HYDRATION Lubricant Eye Drops [REDACTED]

SYSTANE COMPLETE Lubricant Eye Drops [REDACTED]) and SYSTANE HYDRATION Lubricant Eye Drops [REDACTED] are indicated for the temporary relief of burning and irritation due to dryness of the eye. SYSTANE HYDRATION Lubricant Eye Drops may be used to lubricate and rewet daily, extended wear and disposable silicone hydrogel and soft (hydrophilic) contact lenses.

Benefits of a lubricant eye drop include ocular surface protection, dry eye relief, improved visual performance, increased ocular surface retention and lubrication. It also allows re-epithelialization of cells in the ocular surface.

3.2.2 Risk Summary and Mitigation Strategy

Risk management principles have been applied to both the planning and the intended conduct of the clinical investigation, in order to ensure the reliability of the clinical data generated and the safety of the subjects. The clinical investigation process risks are managed through appropriate training and monitoring according to the protocol-specific monitoring plan. IP

risks, including risks associated with use of IP and methods and procedures for application of the IP, are defined in the IB and/or product labeling and are managed through review of safety assessments outlined in this protocol.

The ingredients in the test formulation are biologically inert (i.e., they have no known on-target or off-target biological mechanisms of action). Therefore, no dose-dependent side effects are anticipated. The risks of administering a viscous topical ocular drop include mild transient blurred vision and ocular discomfort. Due to subject variability, there is a risk of allergic reaction to one or more of the components of the test formulation. Patients with any known allergies to any of the components of the formulation are excluded from participation in clinical studies. These anticipated risks are similar to other currently available dry eye drops such as SYSTANE COMPLETE Lubricant Eye Drops [REDACTED] and SYSTANE HYDRATION Lubricant Eye Drops [REDACTED].

There may also be unknown risks to use of IP. Any risk to subjects in this clinical study will be minimized by compliance with the eligibility criteria and study procedures, clinical oversight, and monitoring.

3.2.3 Overall Benefit: Risk Conclusion

Taking into account the measures taken to minimize risk for subjects involved in this study, the potential risks identified in association with FID123300 are justified by the anticipated benefits that may be afforded to subjects for the temporary relief of burning and irritation in persons experiencing dry eye symptoms.

More detailed information about the known and expected benefits and risks and reasonably expected adverse events (AEs) and device deficiencies of FID123300 may be found in the IB.

4 STUDY OBJECTIVES, ENDPOINTS, AND ESTIMANDS

4.1 Primary Objective(s)

Table 4-1 Primary Objectives and Endpoints

Objective(s)	Endpoint(s)
To demonstrate efficacy of a novel lubricant eye drop	Primary 
Change from baseline in Impact of Dry Eye on Everyday Life – Symptom Bother (IDEEL-SB) questionnaire score at Day 30

4.2 Primary Estimand

The treatment effect is to be estimated for the population of adult patients with mild to moderate DED as defined by the protocol inclusion/exclusion criteria. The efficacy is to be

measured using the primary endpoint of the change from baseline in IDEEL-SB questionnaire score at Day 30.

In this single-arm study, an intercurrent event (ICE) may occur with subjects exposing to a concomitant medication or discontinuation of IP (permanent or temporary; due to an AE, device deficiency, and/or noncompliance).

The population-level summary is the mean change from baseline in IDEEL-SB questionnaire score at Day 30, where baseline is defined as the data collected at Visit 1 prior to IP exposure. Change from baseline will be calculated as Day 30 minus baseline.

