5 STUDY DESIGN

5.1 Description of Study Design

This is a phase 3, multicenter, uncontrolled, open label, nonrandomized study conducted at approximately 20 sites in the US. Approximately 185 subjects will be enrolled. All eligible subjects will have mild to moderate DED (inclusion criteria number 4).

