6.2 Inclusion Criteria

Written informed consent must be obtained before any study specific assessment is performed. Upon signing the informed consent, the subject is considered enrolled in the study.

Subjects eligible for inclusion in this study must fulfill **all** of the following criteria:

1. Subject must be at least 18 years of age at the time of informed consent.
2. Subject must be willing and able to understand and sign an IRB/IEC approved informed consent form.
3. Subject must be willing and able to attend all required study visits and complete subjective questionnaires.
4. Subject must exhibit symptoms of dry eye at the Screening visit (IDEEL- SB ≥ 16 and ≤ 65).
5. Subject must have BCVA equal to or better than 20/80 (or ≥ 55 letters score or ≥ 0.6 ETDRS logMAR) in each eye at the Screening visit.
6. Subject must have NITBUT of > 5 and < 10 seconds in each eye at the Screening visit.
7. Subject must meet at least one of the 3 conditions below at the Screening visit (based on the criteria below):
 - a. ADDE as indicated by a TMH of < 0.2 mm
 - b. EDE as indicated by a meibum quality score of ≥ 1 (on a 0 to 3 scale) or meibum expressibility score of > 1 (on a 0 to 3 scale) in either eye lid (lipid deficient (or evaporative) dry eye subgroup) measured by the Meibomian Gland Functionality Test.
 - c. MDE as indicated by meeting both entry criteria (a) and (b) above (mixed dry eye subgroup).
8. Subject must be willing to discontinue use of all artificial tear supplements and use only the study product as directed starting at Visit 2/Day 1.
9. Subject must be willing and able to connect to and use electronic patient reported outcomes with their mobile device to [REDACTED] record daily IP usage information.

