6.5 Screen Failures and Rescreening of Subjects

A screen failure occurs when a subject who consents to participate in the clinical study does not meet inclusion/exclusion criteria. A minimal set of screen failure information is required to ensure transparent reporting of screen failure subjects to meet the Consolidated Standards of Reporting Trials (CONSORT) publishing requirements and to respond to queries from regulatory authorities. Minimal information includes demography, screen failure details, eligibility criteria, and any serious adverse events (SAEs).

Individuals who do not meet the criteria for participation in this study (screen failures) may not be rescreened.

Subjects will not be replaced.

After signing the informed consent form (ICF), subjects will be asked to establish a connection to the electronic patient reported outcomes (ePRO) (inclusion criteria number 9) prior to any other assessments. In the event this connection cannot be established, subjects will be allowed to reschedule the Screening visit within 7 days/1 week. All remaining criteria will be verified after completing inclusion criteria number 9. In case the subject is not willing to reschedule or the Screening visit can't be rescheduled within the specified window, the subject will be considered a screen failure.

Enrollment number may be increased based on the tracking of number of completers.

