9.2 Efficacy Assessments and Procedures

9.2.1 IDEEL-SB Questionnaire

IDEEL-SB Questionnaire score will be completed by the subject at Visit 1/Screening and Visit 4/Exit Day 30 ± 5/Early Exit.

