## 10 APPENDIX

**Table 10-1 Schedule of Study Procedures and Assessments**

Visit	Visit 1 Screening	Visit 2 Baseline	Visit 3 Remote Compliance Check	Visit 4 Exit	Unscheduled Visit	Early Exit
Study Day and Visit Window	2 to 7 days prior to Visit 2	Day 1	Day 14 ± 3 days	Day 30 ± 5 days		
Informed consent	X					
Connect to electronic patient reported outcomes	X 	X		X	(X)	X
Demographics	X					
Medical history	X					
Concomitant medications	X					
Changes to concomitant medications or medical history		X	X	X	X	X
Urine pregnancy test 	X			X	(X)	X
Inclusion/exclusion	X					
Meibomian gland functionality test 	X					
BCVA (OD, OS; logMAR; distance)	X	X		X	(X)	X
IDEEL-SB Questionnaire 	X			X		X
Slit lamp biomicroscopy examination (with corneal staining)	X	X		X	X 	X
Administer IP (IP instillation on site)		X				
Adverse events	X	X	X	X	X	X
Device deficiencies	X	X	X	X	X	X

Visit	Visit 1 Screening	Visit 2 Baseline	Visit 3 Remote Compliance Check	Visit 4 Exit	Unscheduled Visit	Early Exit
Study Day and Visit Window	2 to 7 days prior to Visit 2	Day 1	Day 14 ± 3 days	Day 30 ± 5 days		
Distribute subject instructions		X			(X)	
Dispense IP		X			(X)	
Collect used and unused IP				X	(X)	X
Remote compliance check			X			

(X) Assessments performed as necessary

 Source Only

 Assessment performed as necessary for unplanned IP replacement

 Electronic patient reported outcomes unless otherwise specified by sponsor

 Screening may be rescheduled within 7 days/1 week if connection cannot be established. All remaining criteria will be verified after completing connection.

Signature Page for V-CLN-0196386 v4.0

Signature Page for V-CLN-0196386 v4.0

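### The Visit 1 IDEEL-SB score both decides eligibility and serves as the primary baseline; without a control arm, regression to the mean can move the result either way, and a pre-dose Visit 2 score would remove all or part of that shift

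*Protocol*

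**What the plan says.** **Eligibility.** Protocol 6.2, criterion 4: "Subject must exhibit symptoms of dry eye at the Screening visit (IDEEL- SB ≥ 16 and ≤ 65". Protocol 6.5 adds: "Individuals who do not meet the criteria for participation in this study (screen failures) may not be rescreened". One score therefore decides entry on this criterion.

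**Baseline.** Protocol 4.2: "baseline is defined as the data collected at Visit 1 prior to IP exposure". The general rule in Protocol section 10 and SAP section 4 takes the last value before IP. For the IDEEL-SB that is also Visit 1, so the two rules agree.

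**Schedule.** Protocol 9.2.1: "IDEEL-SB Questionnaire score will be completed by the subject at Visit 1/Screening and Visit 4/Exit Day 30 ± 5/Early Exit". The "IDEEL-SB Questionnaire" rows of Protocol Table 2-2 and SAP Table 10-1 are marked at Visit 1, Visit 4 and Early Exit only. Visit 2 falls 2 to 7 days after Visit 1, is the visit of first instillation, and is marked for "Connect to electronic patient reported outcomes". SAP 5.3 takes Visit 2 as baseline for BCVA and biomicroscopy.

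**Test.** Protocol 5.1: "This is a phase 3, multicenter, uncontrolled, open label, nonrandomized study". Protocol 10.2.1 and SAP 4.2–4.3.1 test whether mean change is below zero with a one-sample t-test at one-sided 0.05. The SAP's success criterion is a reduction from baseline, with no margin in the readable text. SAP Table 1-1 gives 143 completers and about 185 enrolled.

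**The concern.** A single questionnaire score contains chance error. A subject admitted partly because that error lifted the score above 16, or held it below 65, is not expected to carry the same error at Day 30. The mean change from Visit 1 can then differ from zero even if nothing has changed in the subjects.

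The window has two sides. If screened scores sit mostly toward its low end, the lower limit dominates and scores drift down, which favours the product. If they sit toward the high end, the drift is upward and works against it. A control arm selected in the same way would share the shift and cancel it; this trial has none.

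What is at stake is attribution. The objective is to demonstrate efficacy of the drop, so a selection-related fall would be read as product effect and a selection-related rise would hide one.

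**Working it through.** **Inputs.** From the documents: window 16 to 65, n = 143, one-sided 0.05, test against zero. Assumed, because the readable text gives none of them: screened mean m (30 to 45), SD s (10 to 20), Visit 1 to Day 30 correlation r (0.70 to 0.85), a 0–100 scale, no true change. The plan has no figure of its own to reproduce here: 143 cannot be rebuilt without an effect size, SD and power.

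**Threshold.** t(0.95, 142)/√143 = 0.138 SD of change. P(success) comes from the noncentral t. It is below 50% when the expected shift is smaller than the threshold.

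**Normal model, one worked case** (m = 30, s = 20, r = 0.70).
- Limits: (16 − 30)/20 = −0.70 and (65 − 30)/20 = 1.75.
- Mean of those admitted: 30 + 20 × (0.3123 − 0.0863)/0.7180 = 36.29.
- Shift = −(1 − r) × (36.29 − 30) = −0.30 × 6.29 = −1.89 points.
- SD of change = √[(1 − r)² × 154.4 + (1 − r²) × 400] = √(13.9 + 204.0) = 14.76, where 154.4 is the variance of the admitted scores.
- Threshold = 0.138 × 14.76 = 2.04; P(success) = 45%.

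In this model the shift is zero at the window midpoint, (16 + 65)/2 = 40.5.

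**Bounded model** (beta margins on 0–100, Gaussian copula, simulated). The normal model allows impossible scores, so I rely on this one:

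| Screened mean | Shift, SD 18–20 (points) | P(success), SD 18–20 | P(success), SD 10–15 |
|---|---|---|---|
| 30 | −0.6 to −1.5 | 17–29% | 10–26% |
| 35 | −0.2 to −0.4 | 7–10% | 6–10% |
| 37 | about 0 | 5–6% | 5–6% |
| 40 | +0.2 to +0.5 | 2–3% | 3–5% |
| 45 | +0.6 to +1.3 | 0.4–1% | 1–3.5% |

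At SD 18–20 the threshold is 1.4 to 2.3 points. No shift in the grid reaches its own threshold; the largest, −1.5 points, faces 2.3. The zero-shift mean is about 37 to 38.

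In the other direction, suppose the trial had 90% power (assumed; noncentrality 2.94). At screened mean 45, SD 18–20, the upward shift lowers the noncentrality by 0.67 to 1.04, and power falls to about 59–73%.

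**Visit 2 baseline.** The expected change becomes (r₁₃ − r₁₂) × (mean admitted − m), where r₁₂ and r₁₃ are the correlations of Visit 1 with Visit 2 and with Day 30. If the Visit 1 and Visit 2 errors have correlation c, then r₁₂ = r + (1 − r)c and a fraction c of the shift remains:
- c = 0: no shift, P(success) 5% at every mean.
- c = 0.5: half remains; at mean 30, SD 18–20, P(success) is 10–13%.
- c = 0.75: three quarters remains; 13–20%.

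**Share failing the window.** At mean 30 the bounded model puts 25.7% + 4.3% = 30% outside (SD 18), or 29.7% + 6.4% = 36% (SD 20). At SD 10 the share is 7%. The planned loss is 1 − 143/185 = 22.7%.

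**The case against.** **It is a design choice, and sign and size are unknown.** Both are true. The baseline rules agree, every distributional input is assumed, and near the neutral point the change gains little. What stands against this is that a shift of unknown direction in a single-arm test can be measured at a visit that already exists.

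**The largest scenarios strain the plan's own numbers.** If enrolment is counted from consent (Protocol 6.2), 30–36% failing criterion 4 cannot fit within a 22.7% total loss, so mean 30 with SD 18–20 is not compatible. If it is counted from first IP (the enrollment entry in Protocol Table 1-1), it can be. The documents use both definitions, so the case is neither excluded nor established. With few window failures (SD 10), P(success) is 10–13% at mean 30 and 6–7% at mean 35.

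**The remedy leaves other explanations in place.** Correct. Placebo response, open-label expectation and natural course remain, and errors only 2 to 7 days apart may be correlated. The recall period, which bears on this, is not in the readable text.

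**Redacted text may hold a supportive analysis.** Possibly. But the IDEEL-SB rows and 9.2.1 are readable and show no Visit 2 score, so no hidden analysis could use one.

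**Screen-failure counts.** A reader might infer the direction of the shift from how many candidates fail low and how many fail high. That is unreliable: at mean 37, SD 20, about 16% fail low and 10% high with almost no shift. Protocol 6.5 lists what is kept ("Minimal information includes demography, screen failure details, eligibility criteria, and any serious adverse events (SAEs") without saying that the failing side is recorded.

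**Conclusion.** The point holds as an avoidable design weakness. One Visit 1 score is entry test, only pre-dose value and primary baseline, in a trial with no control and a null of zero. Under the assumed inputs, P(success) with no true change runs from about 10–29% at screened mean 30 to 0.4–3.5% at 45, passing 5% near 37–38.

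Three stronger readings are tempting and not supported:
- *The type I error is inflated.* The tested parameter is the mean change itself. A rejection caused by regression is a correct rejection of the null as written; the error lies in crediting the drop.
- *The bias favours the product.* The window is two-sided and no screened mean is given, so the direction is open.
- *Regression alone would produce success.* In every bounded case for means 30 to 45 the shift is below the significance threshold. It changes the chance of a positive result; it does not secure one.

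Confidence is medium: the structure is certain from the text, the size is not. The change is recommended because it is cheap and works in both directions.

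**What to change.** 1. Add the IDEEL-SB at Visit 2, before IP instillation, in Protocol Table 2-2, Protocol 9.2.1 and SAP Table 10-1.
2. Use the Visit 1 score for eligibility only. Do not re-apply the 16 to 65 window at Visit 2, which would select on the new baseline.
3. Define the primary baseline in Protocol 4.2 and the SAP as the Visit 2 pre-dose score. Use Visit 1 only where Visit 2 is missing, and report how many subjects that affects. If 10% fall back, one tenth of the shift remains: 0.06 to 0.15 points at mean 30, SD 18–20.
4. Report the result with the Visit 1 baseline as a sensitivity analysis.
5. Report the Visit 1 to Visit 2 change. It is the more direct guide to the selection shift, and should not be presented as placebo response or 30-day drift.

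**Cost.** One more questionnaire at an existing visit. Other Day 1 activities are partly redacted, so the burden cannot be sized exactly. With independent errors the SD of change rises by about 2–5%; in the worked case, √(2 × 400 × 0.30) = 15.49 against 14.76. An assumed 90% power would fall to about 87–89%; keeping it would take 143 × 1.02² = 149 to 143 × 1.05² = 158 completers.
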